2.0 OBJECTIVES

2.1 Primary Objective

- To determine the effect of the enzalutamide and 5-AR inhibitor on the time to PSA progression in patients aged 65 or older receiving this combination as first line treatment for systemic prostate cancer

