7.6 Follow up Period

All patients will be followed until study closure, death, or patient's decision to withdraw consent. Data will be collected at pre-specified intervals as detailed in the study calendar (see section 8.0) to assess safety and efficacy. After treatment discontinuation, subsequent antineoplastic therapy and survival status will be assessed for the duration of follow up.

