10.0 STATISTICAL CONSIDERATIONS

10.1 Primary End-Point

The primary efficacy end-point for this trial is PSA progression-free survival (PFS) defined as the length of time that a given subject will be alive and free from PSA progression. Median PSA-PFS and 1-year and 2-year PSA-PFS probabilities will be estimated using the Kaplan-Meier method, with 95% confidence intervals constructed based on Greenwood's variance estimator, which is the default approach in SAS 9.3. (66-68) Confidence intervals for the median are given by $\{t : \hat{S}(t) - 0.5\} \leq \chi^2_{\alpha/2} V[\hat{S}(t)]\}$, where t represents all time points satisfying the inequality, $\hat{S}(t)$ is the Kaplan-Meier

estimate of PSA-PFS, $\chi^2_{\alpha/2}$ is a chi-square score with one degree of freedom

corresponding to the chosen confidence level (for 95% confidence $\chi^2_{\alpha/2} = 3.84$), and

$V[\hat{S}(t)]$ is the Greenwood's variance estimator. [64] Confidence intervals for the 1-year and 2-year survival probabilities will be constructed as $\hat{S}(t) \pm z_{\alpha/2} V[\hat{S}(t)]^{1/2}$, where $z_{\alpha/2}$ is

the standard normal score. (67)

It should be noted that in the absence of loss to follow-up (i.e., if vital status and PSA-progression status are known for each subject at the end of the study), $\hat{S}(t)$ coincides

with the observed proportion of subjects alive and without PSA progression by time t and $V[\hat{S}(t)]$ coincides with the usual estimator of the variance of a sample proportion $V[\hat{S}(t)] = [\hat{S}(t)][1 - \hat{S}(t)]/n$, where n is the number of subjects in the study. [65]

Sample size justification: The median PSA-PFS times under null and alternatives hypothesis are assumed to be 1.44 and 3.04 years (the corresponding 1 year PSA-PFS rates are 50% and 72% respectively). Based on this assumption, the one sample log-rank test shows that a sample size of $n=36$ has 82% power (two-sided test with significance level 0.05) to reject the null hypothesis if the median survival time is at least 3.04 years. Taking into account of withdrawal or loss to follow-up (no more than 10% for the first year), we plan to recruit 40 patients in the study.

Expected margin of error (one-half of the confidence width) of the 95% confidence intervals for $S(t)$ can be approximated by $1.96 \sqrt{[\hat{S}(t)][1 - \hat{S}(t)]/n}$. For 1-year and 2-year PSA-PFS this gives $1.96 \sqrt{0.72 \times 0.28/40} = 0.15$, $\sqrt{0.40 \times 0.60/40}$

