respectively. In addition to the number and percentage of subjects alive and without PSA progression at 1 and 2 years of follow-up, we will report separately numbers and percentages of subjects alive and with PSA progression, dead without PSA progression, and dead with PSA progression. The causes of death and the incidence of clinical progression will also be reported.

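### The 1- and 2-year outcome percentages in Section 10.1 make no provision for men censored early, and no planned output gives a censoring-adjusted estimate of PSA progression apart from death

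*Combined protocol and SAP*

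**What the plan says.** Section 10.1 (Primary End-Point) sets the primary estimator: "Median PSA-PFS and 1-year and 2-year PSA-PFS probabilities will be estimated using the Kaplan-Meier method", with Greenwood-based intervals. It then remarks, "It should be noted that in the absence of loss to follow-up", that the Kaplan-Meier estimate reduces to the observed proportion, and it explains the condition as "if vital status and PSA-progression status are known for each subject at the end of the study".

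The sample-size paragraph expects that condition to fail to some degree. It raises 36 to 40 on this ground: "Taking into account of withdrawal or loss to follow-up (no more than 10% for the first year". Section 7.6 gives the end of observation: "All patients will be followed until study closure, death, or" withdrawal of consent. No accrual period or minimum follow-up is stated.

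The section closes with a descriptive breakdown. "In addition to the number and percentage of subjects alive and without PSA progression at 1 and 2 years of follow-up", it says, "we will report separately numbers and percentages of subjects alive and with PSA progression, dead without PSA progression, and dead with PSA progression". It gives no denominator, no category for men not followed to the time point, and no method that adjusts for censoring.

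Objective 2.1 concerns the effect of treatment "on the time to PSA progression in patients aged 65 or older". Sections 6.0, 9.1 and 10.1 define the primary endpoint as PSA-PFS, in which death is also a failure.

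**The concern.** Kaplan-Meier and the four-state breakdown address the same two time points, but only Kaplan-Meier handles censoring. A man lost at month 8 without progression belongs to none of the four states at 1 year. If he stays in the denominator, every state is understated. If he is dropped, the remaining percentages are distorted because men who failed early are kept and men lost early are not. The plan does not choose between these, so the choice could be made after the data are seen.

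Objective 2.1 is about PSA progression and the endpoint is a composite. These men are 65 or older and judged unfit for ADT or at high risk from it, so death without PSA progression is a realistic competing event. The crude table is the only planned output that shows the two apart. The one progression-specific summary in the report would therefore be the one not adjusted for censoring.

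**Working it through.** **Inputs from Section 10.1.** Evaluable n = 36; loss of at most 10% in year 1; recruitment of 40; 1-year PSA-PFS of 72% under the alternative; a 2-year value of 0.40 in the margin-of-error expression.

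**The plan's own figure.** 36 / 0.90 = 40, which reproduces.

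**Assumptions added here.** Loss is independent of outcome and continues at the same yearly rate in year 2 (the plan bounds year 1 only). Rates of 0%, 5% and 10% are shown. The 2-year target is taken two ways: exponential extrapolation, 0.72² = 0.518, and the plan's 0.40. The latter uses a Weibull curve through 72% and 40%, with shape ln(ln 0.40 / ln 0.72) / ln 2 = ln(2.789) / 0.693 ≈ 1.48.

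**Formulas (exponential case).** Failure hazard λ = −ln 0.72 = 0.3285. Loss hazard μ = −ln 0.90 = 0.1054.

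- Kaplan-Meier target: S(t) = exp(−λt).
- Crude, all 40 as denominator: exp(−(λ+μ)t).
- Observed failures: λ/(λ+μ) × [1 − exp(−(λ+μ)t)].
- Crude, known status: (crude of 40) / (crude of 40 + observed failures).

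**At 1 year, 10% loss.** Crude of 40 = 0.72 × 0.90 = 0.648. Failures = 0.757 × 0.352 = 0.267. Known status = 0.648 / 0.915 = 0.71.

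**At 2 years, 10% loss.** Crude of 40 = 0.518 × 0.81 = 0.420. Failures = 0.757 × 0.580 = 0.439. Known status = 0.420 / 0.859 = 0.489.

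Simulation of 4,000 trials of 40 men per setting agreed with these values and supplied the Weibull known-status values. Percentages progression-free:

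| Loss per year | Time and model | Kaplan-Meier target | Crude, of 40 | Crude, known status |
|---|---|---|---|---|
| 10% | 1 year | 72 | 65 | 71 |
| 10% | 2 years, exponential | 52 | 42 | 49 |
| 10% | 2 years, plan's 0.40 | 40 | 32 | 38 |
| 5% | 1 year | 72 | 68 | 71 |
| 5% | 2 years, exponential | 52 | 47 | 50 |
| 5% | 2 years, plan's 0.40 | 40 | 36 | 39 |
| None | either | as target | equal | equal |

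At 10% loss the gap is about 7 points at 1 year and 8 to 10 at 2 years if all 40 are the denominator. It is about 1 point and 2 to 3 points among men of known status. The failure percentages are also affected: with all 40 as denominator, 44% are seen to fail by 2 years against 48% (exponential), or 54% against 60% (plan's 0.40).

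**Against sampling error.** The plan's formula gives 1.96 × √(0.72 × 0.28 / 40) = 0.139 at 1 year and 1.96 × √(0.40 × 0.60 / 40) = 0.152 at 2 years. Every gap above is smaller than that.

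**Share of failure due to death.** The documents give no rate for death without progression. If it were 3% to 10% per year within the total hazard of 0.3285, the 2-year share would run from 0.03 / 0.3285 × 0.482 = 0.044 to 0.10 / 0.3285 × 0.482 = 0.147. That is roughly 4 to 15 of the 48 points of failure.

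**The equivalence remark.** Status known at the end of the study is not status known at time t. If the study closes 18 months after a man enters, his status at closure is known but his 2-year status is not. Section 8.0 also reduces PSA checks, after the first year, to clinical indication for men who stop treatment without progression.

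**The case against.** The strongest reply is that the table is descriptive. No test, decision or stopping rule uses it. The primary conclusion comes from Kaplan-Meier, which handles censoring, and Section 10.1 itself attaches the no-loss condition to the equivalence. This stands, and it limits the point to a supplementary output.

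Three stronger readings are tempting, and the documents do not support them. A reader might infer that the percentages contradict the Kaplan-Meier figures. They need not: the two agree without loss, and otherwise the difference depends on the amount of loss and an unstated denominator. A reader might infer that objective 2.1 is left with no valid estimate. But PSA-PFS is the measure the plan chose for that objective, and its median and 1- and 2-year probabilities are properly estimated. A reader might also infer much larger gaps from staggered entry and study closure. Without an accrual period or minimum follow-up, no size can be attached to that.

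It can also be said that 10% is a ceiling, that the gaps are within the margin of error, and that Section 10.1 also promises causes of death and the incidence of clinical progression. The first is met by showing lower rates. The second compares systematic error with random error; the systematic part is avoidable at no cost. The third does not fill the gap, since clinical progression is not PSA progression. The objection that full multi-state modelling is more than 40 men need is fair, and the fix is kept smaller.

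**Conclusion.** The point holds in limited form. The 1- and 2-year percentages are crude proportions with no rule for men censored earlier, in a plan that expects some censoring. At the planned ceiling, carried into year 2 as an assumption, progression-free percentages would be too low by 7 to 10 points with all 40 as denominator, or by 1 to 3 points among men of known status. At 5% loss the 1-year gaps are about 4 points and 1 point, and without loss there is none. The bias is conditional on censoring.

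The Kaplan-Meier analysis of PSA-PFS, on the usual assumption of independent censoring, is unaffected. What is missing is a censoring-adjusted estimate of PSA progression separate from death, which is the quantity objective 2.1 names. This is an improvement available at no cost, not a threat to the trial's main result.

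**What to change.** 1. In the closing paragraph of Section 10.1, report Aalen-Johansen cumulative incidence of PSA progression and of death without PSA progression, each as the competing event for the other, at 1 and 2 years with 95% intervals. The two add up to one minus the Kaplan-Meier PSA-PFS at the same time, so the supplementary and primary results will agree.
2. Keep the four-state counts as raw counts. Add a row for men censored before the time point and state the denominator.
3. Align the wording of objective 2.1 with PSA-PFS, naming PSA progression alone as a supporting estimate.
4. Limit the equivalence remark to the case where every man's status is known through time t.

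The cost is a few sentences in the plan and a few lines of code. The dates of progression, death and last assessment are already needed for PSA-PFS, so no new data are required.

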10.2 Secondary End-Points

10.2.1 Decline in PSA from Baseline to Nadir

This will be expressed for each subjects in the absolute value and as percentage, displayed for the entire study cohort as a water-fall plot, and summarized with the median (with a 95% confidence interval), first and third quartiles, and the absolute range.

10.2.2 Time to PSA Nadir

This will be expressed for each subjects as the absolute value, displayed for the entire study cohort as a water-fall plot, and summarized with the median (with a 95% confidence interval), first and third quartiles, and the absolute range.

This will be examined by documenting the type and grade of each adverse event (as defined by CTCAE, appendix C) at baseline and at each follow-up visit.(69) These data will be summarized with counts and percentages. In addition, each grade 3 or 4 adverse event will be described separately, and the plausibility of its causation by the study drug combination will be discussed.

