9.2.3 Safety and Toxicity

We will assess the safety and toxicity of this drug combination through routine history and physicals as well as serial monitoring of blood work, all of which will be recorded and reviewed periodically. Adverse events will be defined according to CTCAE version 4.0 (Appendix C).

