11.0 Definition of an Adverse Event

An adverse event or experience is defined as any symptom, sign, illness, or untoward experience (including a clinically significant laboratory finding classified as grade ≥ 3 by the National Cancer Institute's Common Terminology Criteria for Adverse Events [CTCAE]; appendix C) that develops or worsens during the course of the study, whether or not the event is considered related to study drug. Any adverse event should be recorded only after the first dose of study drug is taken. Serious adverse events are recorded from the time the informed consent form is signed.

Where a diagnosis is possible, it is preferable to record it rather than a series of terms relating to the diagnosis.

An abnormality identified during a medical test (e.g., laboratory parameter, vital sign, ECG data, physical exam) should be defined as an AE only if the abnormality meets one of the following criteria:

- Induces clinical signs or symptoms.
- Requires active intervention.
- Requires interruption or discontinuation of study medication.
- The abnormality or investigational value is clinically significant in the opinion of the investigator.

All adverse events, whether or not related to the study drug, must be fully and completely documented.

Adverse events are detected in two ways:

- Clinical: symptoms reported by the patient or signs detected on examination;
- Ancillary Tests: clinically significant abnormalities of vital signs, ECG, laboratory tests, and other diagnostic procedures.

An adverse event **does not** include:

- Medical or surgical procedures (e.g., surgery, endoscopy, tooth extraction, transfusion); however, the condition that leads to the procedure is an adverse event;
- Pre-existing diseases or conditions present or detected prior to the start of study drug administration that does not worsen;
- Situations where an untoward medical event has not occurred (e.g., hospitalization for elective surgery, social and/or convenience admissions);
- Overdose of either study drug or concomitant medication without any signs/symptoms

Relationship to Study Drug: The reasonable possibility of an adverse event's relationship to study drug is to be assessed with careful medical consideration at the time of evaluation of the adverse event. The PI's opinion may be sought in those cases in which the Investigator is unable to make an independent judgment. The following definitions are to be used:

Descriptor	Definition

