[contact]

Follow up reports should include the same information as the initial report with any updates or corrections needed. In addition, they should include the details of study drug administration, and as many details of the serious adverse event as are known, including the date of onset, the intensity, the treatment, and the relationship to study drug. SAE reports must include sufficient detail so that the DSMC can determine the CTCAE term, severity, toxicity grade, expectedness, relatedness, treatment required, and a follow up report documenting resolution and whether there are sequelae. If the patient died, the report should include the cause of death and whether or not the death was related to study drug, as well as the autopsy findings if available.

Do not delay reporting a suspected serious adverse event in order to obtain additional information. Any additional information should be reported in a follow-up to the initial report.

All serious adverse events will be followed until resolution or until the event has stabilized and/or reached a new baseline. All serious adverse events continuing at the completion of the study must be followed to determine outcome. All serious adverse events occurring between the times the patient signs the informed consent and 30 days after the patient's last dose of study drug or prior to the initiation of another systemic antineoplastic therapy, whichever occurs first, must be recorded, reported, and followed up by the investigator using the procedure described above.

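### The causality discussion in the safety analysis names only grade 3 or 4 events and omits fatal ones, and laboratory adverse events are defined inconsistently with no laboratory-value summary to compensate

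*Combined protocol and SAP*

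**What the plan says.** Safety and toxicity is a secondary objective (section 2.2). Its analysis is the safety paragraph that closes section 10.2, listed in the contents as 10.2.3. The method is "documenting the type and grade of each adverse event (as defined by CTCAE, appendix C) at baseline and at each follow-up visit", followed by "These data will be summarized with counts and percentages". No grade cut-off applies to those counts. A further step then follows: "In addition, each grade 3 or 4 adverse event will be described separately, and the plausibility of its causation by the study drug combination" is to be discussed.

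The protocol says in three places what makes a laboratory result an adverse event:

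- **Section 11.0, opening paragraph.** The definition covers untoward experiences, "including a clinically significant laboratory finding classified as grade" 3 or higher.
- **Section 11.0, list.** An abnormality found on a medical test "should be defined as an AE only if the abnormality meets one of the following criteria". The four criteria are clinical signs or symptoms, need for active intervention, need to interrupt or stop study medication, and clinical significance in the investigator's opinion. No grade is mentioned.
- **Section 12.0.** Any unfavorable and unintended sign counts, abnormal laboratory findings included, with no grade or significance condition.

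Section 9.2.3 bases the safety assessment partly on "serial monitoring of blood work, all of which will be recorded and reviewed periodically", and defines adverse events by CTCAE 4.0 with no grade floor. The study calendar schedules blood counts and a comprehensive metabolic panel before and during treatment.

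On deaths, section 10.1 reports causes of death and counts deaths with and without PSA progression. Section 11.4 adds: "If the patient died, the report should include the cause of death and whether or not the death was related to study drug".

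**The concern.** Two gaps affect what the safety report will show.

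**Fatal events.** CTCAE grade 5 is a fatal event, so a sentence naming grades 3 and 4 promises an individual causality discussion for severe and life-threatening events but not for fatal ones. The men enrolled are those whose physicians judge ADT too risky. Competing causes of death are likely in such a group, so attribution matters most for exactly these events.

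**Laboratory toxicity.** Neutropenia, ALT elevation and bilirubin elevation are on the protocol's own list of enzalutamide events (section 3.1.4). Section 10 reports laboratory toxicity only when it has become an adverse event. If the route from result to adverse event differs by section, two sites can each follow the protocol and report different rates from the same blood results. Section 10 plans no summary of the laboratory values that would reveal the difference.

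**Working it through.** The plan states no figure for this point, so the check is a comparison of texts, followed by one illustrative calculation.

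**Step 1: fatal events.**

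| Place | What it covers | Is a fatal event included? |
|---|---|---|
| 10.2.3, counts and percentages | Type and grade of each adverse event | Yes |
| 10.2.3, individual description and causality | Grade 3 or 4 | Not named |
| 10.1, last paragraph | Causes of death; deaths with and without PSA progression | Yes, as cause, without drug-relatedness |
| 11.0 | Severity and relationship to study drug for adverse events of any grade | Yes, case by case |
| 11.3 | Serious adverse event definition | Yes; death is the first criterion |
| 11.4 | Report of each serious adverse event | Yes; cause and relatedness |
| 12.0 | Serious adverse event defined by grade 3 and 4 toxicities | Not named |

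The data on relatedness of death will exist. What is missing is a commitment in the analysis section to describe those events and discuss their cause. Sections 11.3 and 12.0 also define a serious adverse event differently.

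**Step 2: laboratory events.** Two test cases, taken through each definition:

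| Case | 11.0 opening | 11.0 list | 12.0 |
|---|---|---|---|
| Grade 2 ALT rise that interrupts treatment | Not in its laboratory wording | Counted (interruption) | Counted |
| Grade 3 neutropenia: no symptoms, intervention or interruption; judged not significant | Not counted (not significant) | Not counted (no criterion met) | Counted |

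The second case is the decisive one. It fails both rules in section 11.0 and passes in section 12.0.

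**Step 3: is there a backstop?** Section 10.2.3 summarises adverse events only. No part of section 10 tabulates laboratory values by CTCAE grade. The adverse event record cannot supply the baseline grades that 10.2.3 promises either, because section 11.0 records non-serious events only from the first dose. The scheduled pre-study blood tests could supply them for laboratory analytes.

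**Step 4: size, as illustration.** Input: N = 40 (section 6.0). The number of unrecorded events, x, is an assumption; no document gives it. Each one moves the reported incidence by 1/40 = 2.5 percentage points. The intervals are Clopper-Pearson 95%: lower limit = the 0.025 quantile of Beta(x, n − x + 1), upper limit = the 0.975 quantile of Beta(x + 1, n − x). For x = 0 the lower limit is 0 and the upper is 1 − 0.025^(1/40) = 8.8%.

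| True events, all unrecorded | True incidence (95% CI) | Reported |
|---|---|---|
| 1 | 2.5% (0.1 to 13.2%) | 0% (0 to 8.8%) |
| 2 | 5.0% (0.6 to 16.9%) | 0% (0 to 8.8%) |
| 3 | 7.5% (1.6 to 20.4%) | 0% (0 to 8.8%) |

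**The case against.** A reader might infer that the safety analysis leaves out both ends of the grade scale. It does not. The counts cover every recorded adverse event, so fatal events and non-laboratory grade 1 and 2 events are tabulated. The grade restriction applies only to the added narrative.

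A reader might also infer that deaths are never assessed for drug causation. Sections 11.0 and 11.4 require relatedness to be determined, and section 10.1 reports causes. What stands is narrower: the analysis section makes no commitment to present and discuss that information for fatal events.

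Nor does laboratory toxicity enter only through investigator opinion. That is one of four alternative criteria, and section 12.0 has no filter at all. Only one of the three definitions states a grade, so the conflict is a limit against no limit.

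It is fair to say that the opening of section 11.0 uses the word including, which need not exclude lower grades. On that reading the grade 2 ALT case raises no conflict. The grade 3 neutropenia case does not depend on that reading, because the list in section 11.0 is exclusive in form and section 12.0 is not.

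One could add that section 12.0 calls for dose modification after a related grade 3 event, so the result would reach the list through treatment interruption. But that rule applies to adverse events, so it presupposes the classification in doubt, and a dose reduction is not in itself an interruption.

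Finally, the trial has one arm, safety is descriptive, and the committee triggers in section 11.7 use treatment delays and repeated serious events rather than laboratory counts. That stands: no test or stated stopping rule turns on laboratory adverse event rates. It limits the weight of the point but does not remove it, since the rates are themselves the output of a secondary objective.

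**Conclusion.** The point holds in three parts. The narrative and causality sentence in 10.2.3 omits fatal events. The laboratory adverse event definitions in sections 11.0 and 12.0 disagree on whether some graded toxicities count. Section 10 has no laboratory summary by CTCAE grade.

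Reported rates of neutropenia, ALT elevation and bilirubin elevation may be too low and may vary with the definition a site applies. The documents do not show that they will be, because under section 12.0 the same findings count. The size is unknown. At 2.5 percentage points per unrecorded event among 40 men, three events would be the difference between 7.5% and 0%, but three is an assumed number. The primary endpoint is unaffected. This is an inexpensive improvement to a secondary endpoint and does not call the design into question.

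**What to change.** 1. In 10.2.3, replace the grade 3 or 4 restriction with grade 3 or higher, including fatal events.
2. Add to 10.2.3 a table of the worst on-treatment CTCAE grade, and the shift from the pre-study value, for each gradable blood count and metabolic panel analyte. Compute it from the laboratory values, whether or not an adverse event was recorded.
3. Reconcile the laboratory adverse event wording within section 11.0 and between sections 11.0 and 12.0, and the serious adverse event definitions in sections 11.3 and 12.0. Section 12.0 ties dose modification and interruption to these terms, so the choice of definition belongs to the sponsor and investigators. The statistical requirement is that one definition applies throughout.

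The cost is some wording and one extra programmed table from data already scheduled, with no new visits, samples or patients. Reported laboratory toxicity rates may come out higher than under adverse event counts alone. The table also gives a laboratory rate that does not depend on how a site classified the result.
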